## 1.0 INTRODUCTION

### 1.1 BACKGROUND OF THE STUDY

As a highly technical sport, gymnastics integrates multi-dimensional physical quality requirements such as strength, flexibility, coordination, and balance ability, posing extremely stringent challenges to athletes' body control and stability (De Gymnastique, 2023). Athletes need to have excellent physical fitness and be highly concentrated mentally to precisely control every movement detail (Takei, 2007). Due to the quantified scoring criteria with strict thresholds of gymnastics—for example:

Balance beam: Lateral sway exceeding 5cm triggers immediate deductions ( $\geq 0.3$  points per 10cm deviation) (Mkaouer et al., 2012).

Vaulting: Incomplete rotation (e.g., "half-turn" error) results in mandatory score reduction of 0.5-1.0 points (Laws, 2002).

Even slight movement deviations can lead to significant differences in scores. This requires athletes to undergo long-term systematic training, continuously optimize their movement techniques, and improve their movement technique standardization and stability to meet the high-intensity competitive requirements (De Gymnastique, 2023).

Chinese gymnastics has a profound historical and cultural heritage. Over the years, relying on a complete training system, scientific training methods, and the unremitting efforts of athletes, numerous world-class gymnasts have been cultivated (Caine et al., 2013). From the difficult promotion in the early days to winning numerous awards in international top-level competitions today, Chinese gymnastics has achieved huge success, demonstrating the achievements in talent development, technical advancement, and innovation (Jemni, 2017).

The systematic training of beginner gymnasts is the key to the sustainable development of gymnastics. In the initial training phase, beginner gymnasts demonstrate high trainability and a steep learning curve. During this phase, mastering basic skills, such as stability and jumping ability, is crucial for their development (Wang et al., 2013). Therefore, a scientific and well-structured training plan, personalized technical guidance, and a strong emphasis on

fundamental training serve to lay a solid technical foundation for beginner gymnasts. This approach will help them progress steadily in gymnastics, contribute to the ongoing success of Chinese gymnastics, and ensure that China remains a leader on the international stage (Bento-Soares & Schiavon, 2023).

Jumping is a foundational skill in gymnastics, playing a pivotal role across apparatus events such as vault, floor exercise, and balance beam, thereby permeating the entirety of the discipline (Villa et al., 2015). As a universal element in gymnastics, jumping serves as a core indicator of athletes' technical proficiency and competitive excellence. The execution of gymnastic jumps imposes rigorous demands on athletes in three critical dimensions:

1. Explosive Power-Driven Takeoff: Serves as the primary propulsive force propelling athletes into the air (Nitzsche et al., 2022);
2. Mechanical Posture Control: Ensures compliance with aerodynamic principles to minimize air resistance while maintaining spatial body equilibrium during flight (Taylor, 2001);
3. Temporal Precision Management: Dictates optimal force application timing and coordinates movement fluidity throughout the air phase (Tan et al., 2007).

These integrated elements collectively enhance vertical jump height, facilitate the synthesis of strength and technical mastery, ensure stable landings, and enable seamless transitions between movements. In floor exercise, high-difficulty jumping sequences constitute the focal point of performance routines, where both jump elevation and kinematic smoothness directly influence scoring criteria and audience engagement (Makadada et al., 2024). Similarly, vault athletes must exploit springboard elasticity to achieve maximal launch heights, execute complex aerial maneuvers with artistic precision, and finalize with controlled landing postures—any procedural error in this sequence risks falls or score deductions, profoundly impacting overall performance outcomes. Empirical research establishes a strong correlation between vault performance and technical parameters including takeoff force, takeoff angle, and in-air control mechanisms (Yang et al., 2024; Zhao et al., 2024), further underscoring the centrality of jumping in gymnastics. Moreover, sustained, targeted jumping training induces significant improvements in muscular strength and neuromuscular coordination (Alkjaer et al., 2013; Moeskops et al., 2024), providing a physiological foundation for optimizing jump quality.

Stability is also of paramount importance in gymnastics. It is the key for athletes to achieve excellent results and ensure their own safety (Mkaouer et al., 2017). The ability of gymnasts to maintain body control after jumping or during movement transitions directly affects the error rate. Research shows that even slight instability may lead to a 15% to 20% increase in deductions (Leandro, 2018). In the gymnastics competition scoring system, although difficulty is important, the quality of movement execution is equally crucial. Stability is the core indicator for measuring the quality of movements. High-difficulty movements accompanied by body imbalance or unstable center of gravity will lead to significant deductions (Sands, 2000).

From a safety perspective, research shows that enhancing stability can effectively reduce injury risks, particularly in high-impact landings and repetitive movements prevalent in gymnastics (Harry-Leite et al., 2022). For example, a longitudinal study on balance beam athletes found that those who incorporated proprioceptive training into their routines had a 34% lower incidence of falls during competitions (Mekić et al., 2024). In balance beam events, athletes must perform complex movements on a narrow apparatus requiring extreme stability. According to statistics from the 2020 FIG World Championships, 42% of balance beam routine failures were directly attributed to stability impairments (de Oliveira et al., 2022).

Similarly, in vault landings and floor exercise transitions, stability is critical for maintaining control over movements. This is supported by biomechanical analyses showing that athletes with superior core stability achieved 12% better angular momentum control during tumbling passes (Small & Neptune, 2024). Furthermore, a systematic review of Olympic-level performances revealed that stability-based training regimens reduced landing injury rates by 28% compared to traditional training methods (İpek Dongaz et al., 2024). Studies have demonstrated that core stability training significantly enhances gymnasts' balance and control during complex movements (Nazari & Hooi, 2019), underscoring the necessity of stability training within comprehensive gymnastics training systems.

In gymnastics, both dynamic and static balance play a crucial role in enhancing athletes' body control and coordination (Poliszczuk et al., 2012). An athlete's balance ability largely determines whether they can successfully complete a series of movements while ensuring safety and artistic quality (Zemková & Zapletalová, 2022). Balance movement training can develop athletes' sense of balance and coordination, enhance the strength of the core muscle

group and body control. Various methods, such as stability training, balance apparatus training, and movement decomposition training, provide both theoretical and practical foundations for improving gymnasts' stability. These approaches highlight the crucial role of targeted balance training in significantly enhancing athletes' overall performance (Ahmadabadi et al., 2015).

Although the significance of balance training has been widely acknowledged, research on the combined effects of static and dynamic balance training for beginner Chinese gymnasts remains limited (Yu et al., 2024). Current studies primarily focus on single training modalities or elite athletes, frequently neglecting the specific training needs of beginner gymnasts. Beginner gymnasts are in a developmental stage of physical fitness and motor skills, which differs significantly from that of elite athletes. (Goodway & Robinson, 2015). Their muscle strength, joint flexibility, and neuromuscular coordination are still developing, requiring targeted training methods to support their progress (Omorczyk et al., 2018).

Balance training is the foundation of the gymnastics training system, integrating neuromuscular control, movement coordination, and proprioception (U. Granacher et al., 2010). The two main types of balance training commonly used in gymnastics training are static balance training and dynamic balance training. For static balance training, athletes are required to maintain specific postures on the apparatus, which helps them develop the ability to control their bodies in a stationary state (Marchenkova et al., 2021). On the other hand, dynamic balance training focuses on maintaining balance during movement. In the training, it simulates the challenges that athletes encounter during processes such as rotations and dismounts (Wang et al., 2024), helping them adapt to changes in the center of gravity and improve their ability to control movement transitions and recover from unstable landings. Research shows that compared with single training methods, combining static and dynamic balance training can produce better results (Eleni G Fotiadou et al., 2009). A study in 2023 showed that compared with athletes who only received static or dynamic training separately, a group of athletes who received a comprehensive balance training program improved their balance-related performance indicators by 20% (Lockard & Gable, 2023). This comprehensive training method can improve the stability of athletes when they complete complex gymnastics movement sequences (for example, the complex rotational movements in somersaults, which require precise spatial orientation and angular momentum control during the three-dimensional rotation of the body;

or the dynamic takeoffs and landings in jumps, where athletes must instantaneously adjust the center of mass and implement corrective kinematic strategies to stabilize the body both in the air and upon landing) (Ringhof & Stein, 2018).

Since 2020, remarkable progress has been made in the balance training of gymnasts (Farana et al., 2023). These studies have systematically investigated how different training methods affect the balance ability and related physical qualities of gymnasts. In competitive gymnastics, Bosu ball training (in which athletes perform dynamic and static postures on the ball to improve their balance ability and proprioception) has been proven to be able to improve the activation pattern of trunk muscles (Gao et al., 2024). Similarly, compared with traditional flat surface training, balance board training (maintaining stability on an unstable surface) shows better effects in terms of balance control (Behm et al., 2015). At the same time, balance beam (basic skill) training plays a crucial role in cultivating balance ability in complex movement routines and enhancing mental concentration under high-pressure conditions, which is evidenced by its ability to reduce the movement errors of beginner gymnasts. (Mahdi et al., 2024). Studies have shown that these methods can significantly enhance the trunk muscle strength of gymnasts (Ekaitz Dudagoitia Barrio et al., 2022). However, it cannot be ignored that there are still limitations in the existing research in two key aspects. Firstly, most of the studies focus on specific events such as the balance beam, vault, and uneven bars (McAuley et al., 1985), and there is limited exploration of the training adaptability of different apparatus events. Secondly, there is insufficient evidence regarding the long-term effects of static-dynamic balance training on beginner groups, especially Chinese gymnasts (Urs Granacher et al., 2010).

In the field of gymnastic balance training, research achievements have been continuously emerging (Barker et al., 2018). In particular, the latest breakthrough in motion capture technology has deeply revealed the internal mechanism of expected postural adjustment during dynamic transitions (Burton et al., 2024). However, despite the significant achievements of these studies in specific fields, research across methodologies and cultural backgrounds still remains insufficient (Kueh et al., 2021).

With the continuous development of gymnastics, the requirements for athletes are increasingly growing, and the scientific and effectiveness of training methods have become more and more crucial (Armstrong & Relph, 2021). Therefore, this study aims to fill this gap by systematically

exploring the impact of the combination of static and dynamic balance training on the stability and jumping skills of beginner gymnasts (Gaspari et al., 2024). By revealing the effects and mechanisms of this training method, this study will provide scientific guidance for coaches and optimize the training plans for beginner gymnasts (Jimenez-Diaz et al., 2021).

Meanwhile, through customized training plans, this study will support the formulation of effective coaching strategies, bridge the gap between basic skills and advanced performance, and promote the progress of talent cultivation in Chinese gymnastics (Bergeron et al., 2015).

## **1.2 PROBLEM STATEMENT & STUDY RATIONALE**

During the initial stage of gymnastics learning, the improvement of athletes' stability and jumping ability represents a critical milestone toward mastering complex gymnastics techniques (Hrysomallis, 2011). Static and dynamic balance training have been shown to significantly enhance athletic performance and prevent sports injuries (Granacher & Behm, 2023). However, current research primarily focuses on elite athletes or individuals with sports injuries, with insufficient attention to the unique needs of beginner gymnasts (Borghuis et al., 2008). Furthermore, the differential effects of various types of balance training remain underexplored, particularly the comparative effects of combined static and dynamic balance training versus single-task balance interventions (Behm & Colado, 2012). Previous studies have demonstrated that static balance training primarily enhances static postural control (e.g., standing on one leg with eyes closed), effectively reducing the risk of falls, while dynamic balance training focuses on improving neuromuscular coordination during transitional movement phases (e.g., the moment of landing after a jump), thereby enhancing dynamic control (Abdelmohsen et al., 2025). Based on this, the present study, grounded in motor control and balance theories (Shumway-Cook & Woollacott, 2007), aims to investigate the effective mechanisms by which combined static and dynamic balance training improves jumping performance and enhances movement stability in beginner gymnasts.

### **1.3 RESEARCH QUESTIONS**

- (1) What are the differential effects of static, dynamic, and static-dynamic combined balance training on the stability (measured by the maximum distance of single-leg extension and the bilateral symmetry index in the Star Excursion Balance Test (SEBT)) of beginner gymnasts?
- (2) Do static, dynamic, combined balance training induce distinct improvements in jumping mechanics (CMJ/SLCMJ: jump height, PF, RFD, impulse) and kinetic efficiency (jump height/GRF ratio), and does combined training show superior neuromuscular adaptations?
- (3) Among static, dynamic, and static-dynamic combined balance training modalities, which one most effectively minimizes the center of mass (COM) offset distance, body sway amplitude, and landing impact force—while maximizing rotational smoothness and single-leg balance duration—in beginner gymnasts when they perform 360° single-leg standing pirouettes and 360° straight-body jump turns, with all outcomes quantified by 3D motion capture technology?

### **1.4 OBJECTIVES OF THE STUDY**

#### **1.4.1 General objective**

To determine the effectiveness of static, dynamic, and combined static-dynamic balance training interventions on the stability and jumping skills of beginner gymnasts, as well as their impact on the biomechanics and motor performance of gymnastic movements.

#### **1.4.2 Specific objective**

- (1) Evaluate the effects of static balance training, dynamic balance training, and combined static-dynamic balance training on the stability of beginner gymnasts. Quantify the maximum single-leg extension distance (reflecting lower limb support force) and the bilateral symmetry index (reflecting neuromuscular coordination) through the SEBT test to compare the differential effects of different training modes on stability improvement.
- (2) To evaluate the effects of static balance training, dynamic balance training, and combined static-dynamic balance training on the jumping skills of beginner gymnasts, this study measures the changes in data (such as jumping height, peak force, rate of force development, and impulse) of athletes during countermovement jump (CMJ) and single-leg countermovement jump (SLCMJ) before and after training. Through these measurements, it

aims to deeply analyze the mechanism of action of different training modes in enhancing the jumping ability of beginner gymnasts.

(3) This study aims to explore the improvement effects of static balance training, dynamic balance training, and combined static-dynamic balance training on the performance of gymnastic movements (such as standing 360° single-leg turn and straight jump 360° turn). Through three-dimensional motion capture technology, the study assesses beginner gymnasts in terms of center of gravity deviation distance, body oscillation amplitude, rotation smoothness index, and landing impact force during the standing 360° single-leg turn. For the straight jump 360° turn, it conducts quantitative analysis based on center of gravity deviation distance, joint angle variation, vertical jump efficiency, and landing impact force.

## **1.5 HYPOTHESES OF THE STUDY**

Statistical Hypotheses for the First Part:

HA1: There is a significant improvement in the stability of beginner gymnasts (as measured by the 8-Point Star Offset Test) following static balance training, dynamic balance training, or combined static-dynamic balance training interventions.

H01: There is no significant improvement in the stability of beginner gymnasts (as measured by the 8-Point Star Offset Test) following static balance training, dynamic balance training, or combined static-dynamic balance training interventions.

Statistical Hypotheses for the Second Part:

HA2: There is a significant improvement in the jumping skills of beginner gymnasts (as measured by Countermovement Jump and Single-leg Countermovement Jump) following static balance training, dynamic balance training, or combined static-dynamic balance training interventions.

H02: There is no significant improvement in the jumping skills of beginner gymnasts (as measured by Countermovement Jump and Single-leg Countermovement Jump) following static balance training, dynamic balance training, or combined static-dynamic balance training interventions.

Statistical Hypotheses for the Third Part:

HA3: Static balance training, dynamic balance training, or combined static-dynamic balance training significantly enhances gymnastic performance movements (as measured by Standing Single-leg 360 ° turn and Straight jump 360 ° turn), as captured using 3D motion capture technology.

H03: Static balance training, dynamic balance training, or combined static-dynamic balance training does not significantly enhance gymnastic performance movements (as measured by Standing Single-leg 360 ° turn and Straight jump 360 ° turn), as captured using 3D motion capture technology.

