### 3.2 Research design

This study employs a four-arm parallel-group randomized controlled trial design to evaluate the efficacy of static, dynamic, and combined balance training on beginner gymnasts' stability and rotational performance. Figure 2 illustrates the experimental flow, including recruitment, randomization, interventions, and outcome assessments.

[figure not shown]

Figure 2 Flow chart of the experimental design

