### **3.6 Sample Size Estimation**

Using G - power 3.1 (Figure 10), the study focuses on time (within - subject factor), group (between - subject factor), and their interaction effects. The effect size is set to medium (0.35), with an alpha value of 0.05 and a statistical power of 0.80. A total of four groups will be included (static balance, dynamic balance, combined static and dynamic balance, and a control group), with measurements conducted twice, pre - and post - intervention. The calculated sample size is 52 participants. Considering a dropout rate of 15%, 60 participants will be recruited. Participants will be randomly assigned to four groups, with 15 participants in each group. Since the total dropout rate applies uniformly and participants are equally distributed across the four groups, each group's dropout rate is also 15%.

[figure not shown]

Figure 10 Flow chart of the G-power

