### **3.8 INTERVENTION METHODS**

Participants in the SG intervention group will complete an 8-week training program consisting of Plank Support, Single-Leg Stance, Eyes-Closed Double-Leg Stance, and Half-Squat Exercise. The DG intervention group will engage in Landing Control Training, Balance Beam Walking, jumping onto the Balance Beam, and Squat-to-Stand Exercises. The SDG intervention group will perform Plank Support, Single-Leg Stance, Eyes-Closed Double-Leg Stance, Half-Squat Exercise, Landing Control Training, Balance Beam Walking, jumping onto the Balance Beam, and Squat-to-Stand Exercises. Each exercise will be repeated 3 times or the corresponding number of times per session, with each session lasting 15 minutes (including 30 minutes of dynamic and static balance exercises), conducted twice a week for 8 weeks. All participants will enroll simultaneously, and each group will be guided by qualified instructors. Before and after each training session, participants will wear a heart rate monitor (Xiaomi Smart Band) on their wrist to ensure adherence to the prescribed training intensity outlined in Tables 13, 14, and 15. Additionally, participants may adjust their limb positions and movement intensity based on their physical condition. At the end of each session, training logs will be completed to document the activities. Only data from participants who adhere to at least 80% of the prescribed training program will be included in the analysis.

Participants in the control group (CG) will continue their regular training routine as detailed in Tables 7 and 8. They will be advised to maintain their usual daily activities without incorporating any additional exercises.

Table 13: Static balance training intervention content (n=15)

Week	content	Minutes/ Groups	Inter-group Rest Duration	Training duration	HR Monitoring Indicators	Heart Rate Monitoring Equipment	Intervention time	Heart rate range	Equipment
W 1	baseline test								
W 2-3	①Double leg stand ②Single leg stand	1/3	Rest for 2 minutes	15minutes	Resting Heart Rate (Before Training)/Maxi mum Heart Rate/Maximum Heart Rate	Xiaomi Smart Band	8 weeks, 2 times per week, 15 minutes each time	80bpm-100bpm	Balance board、BOSU ball
W 4	①Eyes-closed double-leg stance ②Plank support	1/3	Rest for 2 minutes	15minutes				80bpm-110bpm	Balance board 、 BOSU ball、 Gymnastic mat

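### The hypotheses in section 1.5 name no comparator, so a gain shared with the control arm could satisfy them in a controlled, comparative trial

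*Protocol*

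**What the plan says.** Protocol section 1.5 lists three pairs of statistical hypotheses. HA1 reads "There is a significant improvement in the stability of beginner gymnasts (as measured by the 8-Point Star Offset Test) following static balance training" and continues with dynamic or combined training as alternatives. HA2 has the same form for the jump tests. HA3 says that any of the three modes "significantly enhances gymnastic performance movements". The nulls mirror these statements. None of the six mentions the control arm or sets one mode against another.

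The rest of the protocol is comparative:

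- Section 3.2: "This study employs a four-arm parallel-group randomized controlled trial design to evaluate the efficacy of static, dynamic, and combined balance training".
- Section 3.8: "Participants in the control group (CG) will continue their regular training routine as detailed in Tables 7 and 8".
- Section 1.3, question 2: "does combined training show superior neuromuscular adaptations". Question 3 asks "which one most effectively minimizes the center of mass (COM) offset distance".
- Section 1.4.2, objective 1, intends "to compare the differential effects of different training modes on stability improvement".
- Section 3.6: "the study focuses on time (within - subject factor), group (between - subject factor), and their interaction effects".
- Tables 16 to 20 carry columns for a two-way repeated-measures ANOVA and Bonferroni p-values.
- Section 3.8.3 claims to identify the most effective training strategy. The analyses it lists, in an open list, are descriptive, demographic, correlation and factor analyses.

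**The concern.** A hypothesis about improvement after training is a pre-post statement. It is true if the trained arms get better for any reason, including reasons that act equally on the controls. Here such reasons are easy to name. All arms are beginners, all take the routine gymnastics classes, and all repeat the same tests. Section 1.1 itself expects beginners to learn fast. Judged as worded, such a gain would be reported as success for balance training. The group-by-time term would not count it, so the same data could support opposite conclusions.

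The second gap is that no hypothesis expresses a difference between modes. All three alternatives could be accepted without settling whether combined training is superior or which mode works best, which is what section 1.3 asks.

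**Working it through.** **1. Wording against design.** HA1 and HA2 correspond to a within-arm change or a time effect. Of the three terms in section 3.6, only time matches that reading. The four-arm design, the control arm and the questions in 1.3 call for differences between arms in change, which is the group-by-time term and its contrasts. No passage ties a hypothesis to that term.

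**2. The plan's own figure.** Section 3.6 gives f = 0.35, alpha 0.05, power 0.80, four groups, two measurements and N = 52. For the interaction, lambda = f² × N × m/(1 − rho). With rho = 0 this is 0.35² × 52 × 2 = 12.74 on 3 and 48 df, giving power 0.831; N = 52 is the smallest multiple of four that reaches 0.80. The between-group factor at rho = 0 also gives 52, while the time effect alone would need 36. The correlation used is not readable, so this is only indicative, but 52 is compatible with sizing on the interaction.

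**3. What a shared gain does.** Inputs: 13 per arm (52/4). Assumed, because the protocol gives none: no training effect, a gain of 0.4 baseline SD in every arm, and pre-post correlation rho = 0.3/0.5/0.7. The SD of change is sqrt(2(1 − rho)) = 1.18/1.00/0.77.

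- Time effect, F(1,48), lambda = 52 × 0.4²/(2(1 − rho)) = 5.94/8.32/13.87: significant with probability 0.67/0.81/0.95.
- Group-by-time, F(3,48), no true difference: rejects in about 5% of simulated trials.
- Time significant and group-by-time not: about 0.63/0.77/0.91 (20,000 simulated trials per case; a repeat with 100,000 gives 0.76 for the middle value).
- Arm-by-arm reading, two-sided paired t-test with n = 13: 0.20/0.26/0.40 per arm. At least one of the three training arms, 1 − (1 − p)³: 0.49/0.60/0.79.

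**4. Range for the time effect.**

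| Shared gain (SD) | rho 0.3 | rho 0.5 | rho 0.7 |
|---|---|---|---|
| 0 | 0.05 | 0.05 | 0.05 |
| 0.2 | 0.22 | 0.29 | 0.45 |
| 0.3 | 0.43 | 0.56 | 0.78 |
| 0.4 | 0.67 | 0.81 | 0.95 |
| 0.5 | 0.85 | 0.94 | 0.995 |

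**5. What the comparative claims would need.** The detectable pairwise difference in change at 80% power, 13 per arm and 48 df is approximately (t for alpha/(2 × number of contrasts) + t for 80% power) × SD of change × sqrt(2/13). For five contrasts and rho = 0.5 this is (2.68 + 0.85) × 1.00 × 0.392 = 1.39 SD. Exact values:

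| Contrasts adjusted | rho 0.3 | rho 0.5 | rho 0.7 |
|---|---|---|---|
| 3 | 1.55 | 1.31 | 1.01 |
| 5 | 1.64 | 1.39 | 1.08 |
| 6 | 1.68 | 1.42 | 1.10 |

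**The case against.** The strongest reply is that the protocol plainly intends a between-group analysis. Section 3.6 names group and interaction effects, Tables 16 to 20 put all four arms into one ANOVA with Bonferroni, and N = 52 fits the interaction. This makes the fault repairable, but it does not remove it: no hypothesis is linked to the interaction, the tables do not say which effect decides, and section 3.8.3 does not carry the ANOVA over.

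A second reply is that the pooled time effect includes the controls, whom the hypotheses do not mention. That is fair. With the three training arms only (N = 39, F(1,36)) the probabilities become 0.54/0.68/0.88, and with Bonferroni over three arms the arm-by-arm figures fall to 0.26/0.35/0.54. The illustration shrinks, but its direction does not change.

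Two further points stand in part. HA3 uses causal wording that, in a controlled trial, may be read as relative to control; it is still true that no comparator is named. In section 1.4.2 only objective 1 speaks of differential effects, so the clash with the objectives is narrower than the clash with section 1.3.

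Finally, the list in 3.8.3 is open, and testing detail may be left to an analysis plan. Hypotheses belong in the protocol, however, and a plan that followed these faithfully would inherit the fault. The correlation item does set training method against improvement, but with four unordered arms it is not a formal test of which arm gained more; factor analysis describes covariance among measures.

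**Conclusion.** The concern holds and should be fixed. HA1 and HA2 are pre-post statements, HA3 lacks a comparator, and none of the three states a contrast between modes; this conflicts with the controlled design and with the questions in section 1.3. Under the assumed shared gain of 0.4 SD with no training effect, the two readings disagree in roughly 63% to 91% of trials. For shared gains of 0.2 to 0.5 SD, the chance of a significant time effect runs from 0.22 to above 0.99. These figures rest on assumed gains and correlations; the finding on the wording does not.

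**What to change.** Restate HA1 to HA3 and their nulls as between-arm differences in change: each training arm against control, and between training modes as section 1.3 asks. In section 3.8.3, name the two-way repeated-measures ANOVA already shown in Tables 16 to 20, make the group-by-time interaction the deciding test, and follow it with Bonferroni-adjusted between-arm contrasts of change. Other between-arm procedures would also be acceptable; what matters is that a between-arm test decides. Label the correlation and factor analyses exploratory.

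The edit is to wording only and needs no new data. The stated N of 52 can stay, since it reproduces for the interaction at zero correlation. The real cost is fewer and harder claims: with five adjusted contrasts, a pairwise difference in change must be about 1.1 to 1.6 SD for 80% power, so the pairwise questions remain poorly powered unless effects are large. The change should be made before data collection, which Table 22 dates 1/9/2026, so that the success criterion is not chosen after the results are seen.
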